**List of Appendices**

**Table of Abbreviations or Term**

Abbreviation or Term	Definition/Explanation
AE	adverse event
BDSG	Biomedical Data Stewardship Governance
BOR	best overall response
CI	confidence interval
CRF	case report form
CNS	central nervous system
CR	complete response
CSR	clinical study report
CT	computed tomography
CTCAE	Common Terminology Criteria for Adverse Events
DILI	drug-induced liver injury
DLRT	Dose Level Review Team
DLT	dose limiting toxicity
DOR	duration of response
DRE	Disease-related events
ECG	Electrocardiogram
EDC	electronic data capture
End of Study for Individual Subject	Defined as the last day that protocol-specified procedures are conducted for an individual subject (ie, the date the subject withdraws full consent/assent from the study, completes the safety follow-up visit or long-term follow-up [whichever is later] or death).
End of Study (primary completion)	The primary completion date is defined as the date when the last subject is assessed or received an intervention for the final collection of data for the primary endpoint(s), whether the study concluded as planned in the protocol or was terminated early. The primary completion date is anticipated to occur 35 days after the last subject has enrolled and received at least 1 dose of talimogene laherparepvec .
End of Study	The end of study date is defined as the date when the last subject across all sites is assessed or receives an intervention for evaluation in the study (ie, last subject last visit), following any additional parts in the study (eg, long-term follow-up), as applicable.
End of Treatment	defined as the last assessment for the protocol-specified treatment phase of the study for an individual subject
FDA	Food and Drug Administration
GM-CSF	granulocyte macrophage colony-stimulating factor
HSV, HSV-1	herpes simplex virus, herpes simplex virus type 1

Abbreviation or Term	Definition/Explanation
HCP	Health Care Professional
IP	Investigational Product
IPD	Important Protocol Deviations
irRC-RECIST	Immune-related Response Criteria (irRC) simulating Response Evaluation Criteria in Solid Tumors (RECIST)
L-CR	Lesion complete response
L-DOR	Lesion duration of response
LLOQ	Lower Limit of Quantification
L-ORR	Lesions objective response rate
L-PR	Lesion partial response
L-TTR	Lesion time to response
MedDRA	Medical Dictionary for Regulatory Activities
ORR	objective response rate
OS	overall survival
PD	progressive disease
PFS	progression-free survival
PFU	plaque-forming unit
PR	partial response
QT interval	QT interval is a measure of the time between the start of the Q wave and the end of the T wave in the heart's electrical cycle as measured by ECG.
QTc	QT interval corrected for heart rate using accepted methodology
RECIST	Response Evaluation Criteria in Solid Tumor
SAE	serious adverse event
SD	stable disease
SOC	System organ class
Source Data	Information from an original record or certified copy of the original record containing patient information for use in clinical research. The information may include, but is not limited to, clinical findings, observations, or other activities in a clinical trial necessary for the reconstruction and evaluation of the trial. Source data are contained in source documents (original records or certified copies). (ICH Guideline [E6]). Examples of source data include subject identification, randomization identification, and stratification value.
Study Day 1	defined as the first day that Talimogene laherparepvec administered to the subject
TEAE	Treatment-Emergent Adverse Event
TESAE	Treatment-Emergent Serious Adverse Event

---

Abbreviation or Term	Definition/Explanation
ULN	Upper Limit of Normal
[REDACTED]	[REDACTED]

## 1. Introduction

The purpose of this Statistical Analysis Plan (SAP) is to provide details of the statistical analyses that have been outlined within the protocol **amendment 3** for talimogene laherparepvec Study 20110261 dated **12 June 2020**. The scope of this plan includes the primary analysis and the final analysis that are planned and will be executed by the Biostatistics department unless otherwise specified.

The clinical study report (CSR) will be written based on the results of the primary analysis. Data collected and analyzed in Amgen-owned databases and systems will adhere to approved Data Element Standards and International Case Report Form (CRF) Standards established by Biomedical Data Stewardship Governance (BDSG).

## 2. Objectives

### 2.1 Primary

To evaluate the safety and tolerability of talimogene laherparepvec, as assessed by incidence of dose-limiting toxicities (DLT), in pediatric subjects with advanced non-central nervous system (CNS) tumors that are amenable to direct injection.

[figure not shown]
### 2.2 Secondary

- To evaluate the anti-tumor activity of talimogene laherparepvec, as assessed by overall response rate (ORR), duration of response (DOR), time to response (TTR), time to progression (TTP), progression-free survival (PFS) using immune related Response Criteria Simulating Response Evaluation Criteria in Solid Tumors(RECIST 1.1) [Modified irRC RECIST], and overall survival (OS).

### 2.3 Safety

To evaluate the safety and tolerability of talimogene laherparepvec

### 2.4 Exploratory

### 3. Study Overview

#### 3.1 Study Design

This is a phase 1, multicenter, open label study of talimogene laherparepvec in pediatric subjects with advanced non-CNS tumors that are amenable to direct injection in the clinical setting.

Approximately **18 to 24** pediatric subjects are expected to be enrolled and **treated with at least 1 dose of talimogene laherparepvec** into 2 cohorts stratified by age (permissible based on the incidence of DLTs, a minimum of **18 dosed** subjects total **for the primary analysis**) as follows:

- Cohort A1 (12 to  $\leq$  21 years of age)
- Cohort B1 (2 to  $<$  12 years of age)

Initially, 3 subjects 12 to  $\leq$  21 years of age are to be enrolled and treated at 100% of the recommended adult dose regimen of talimogene laherparepvec (Cohort A1). The first dose administered will be up to 4.0 mL of  $10^6$  PFU/mL followed by a dose of up to 4.0 mL of  $10^8$  PFU/mL 21 days (+3 days) later. Subsequent doses of up to 4.0 mL of  $10^8$  PFU/mL will be administered approximately every 14 days ( $\pm$  3 days) thereafter (see protocol Section 6.2.1.1). The DLT evaluation period is 35 days from the initial administration of talimogene laherparepvec. Rules for DLT evaluation are described in Section 6.2.1.2.1 of the protocol. The dose level review team (DLRT) will review the safety data of the first 3 subjects in the older age cohort A1 to decide if the younger age cohort B1 can be opened for enrollment. If none of the first 3 DLT-evaluable subjects in cohort A1 experiences a DLT then cohort B1 will be opened for enrollment and treatment at the same dose level per the section Study Design and Treatment Schema of the protocol. If a DLT occurs in the first 3 DLT-evaluable subjects in the older age cohort (A1 or A2), the younger age cohort will not open until a DLT rate  $<$  33% is observed with at least 6 DLT-evaluable subjects in the older age cohort (A1 or A2). If any of the first 3 subjects in cohort A1 experiences a DLT, the DLRT will make a recommendation on whether an additional 3 subjects should be enrolled in cohort A1.

Cohort A1 or B1 can enroll up to a maximum of **18 subjects treated with at least 1 dose of talimogene laherparepvec with at least 9 DLT-evaluable subjects in cohort A1**. In the case of dose de-escalation, the minimum number of DLT-evaluable subjects at the de-escalated dose will be **6** (permissible based on the incidence of DLTs). After an age cohort is closed for further enrollment, if  $<$  33% of all DLT-evaluable subjects in

the cohort experiences a DLT at a dose level, the dose will be declared safe for the cohort.

If dose de-escalation is needed and if permissible based on the incidence of DLTs, a minimum of 6 additional DLT evaluable subjects will be enrolled and treated at a lower dose level of talimogene laherparepvec (Dose Level -1). The initial dose administered will be up to 4.0 mL of  $10^6$  PFU/mL followed by dose of up to 4.0 mL of  $10^6$  PFU/mL 21 days (+ 3 days) later. Subsequent doses of up to 4.0 mL of  $10^6$  PFU/mL will be administered approximately every 14 days ( $\pm$  3 days) thereafter (see Table 1). Dose de-escalation cohorts will obey the following naming convention, based on age at baseline, and the same DLT rules will be applied to the de-escalated cohorts:

- Cohort A2 (12 to  $\leq$  21 years of age)
- Cohort B2 (2 to  $<$  12 years of age)

**Table 1. Dose De-escalation**

Dose Level	Initial Dose	Subsequent Doses
1	$10^6$ PFU/mL	$10^8$ PFU/mL
-1	$10^6$ PFU/mL	$10^6$ PFU/mL

### 3.1.1 Tumor Response Assessment

Assessment of tumor response will be performed according to modified irRC-RECIST (Nishino et al, 2013 and Nishino et al, 2014). Details can be found in protocol Appendix D.

#### 3.1.1.1 Safety Follow-up

Adverse events will be collected as described in protocol Section 9.2. All subjects will complete a safety follow up visit approximately 30 (+ 7) days after the last dose of study treatment. Adverse events and any concomitant medications associated with adverse events that occur 30 (+ 7) days following cessation of treatment will be reported, followed, and recorded in the case report form (CRF).

#### 3.1.1.2 Long-term Follow-up

After the safety follow up visit, all subjects will enter the long term follow up. Subjects will be followed for survival and use of subsequent anticancer therapies every 12 weeks ( $\pm$  28 days) from the safety follow-up **visit** until death, subject or legally acceptable representative withdraws full consent/ assent, or up to approximately 24 months after the last subject is enrolled in the study **whichever occurs first**. In addition, talimogene

laherparepvec related adverse events that occur through the end of the long term follow up will be reported.

### 3.2 Sample Size

The sample size of **18 to 24 subjects will be enrolled and treated with at least 1 dose of talimogene laherparepvec with at least 9 DLT-evaluable subjects in cohort A1. For age cohort opening and dose de-escalation, criteria from 3+3 phase 1 designs assuming a true DLT incidence rate < 33% is used. Minimum sample size with age between 2 and 12 years cohort is not required.**

[figure not shown]
A dose level will be considered safe for a cohort if < 33% of all DLT evaluable subjects in a given cohort experiences a DLT (**minimum of 6 DLT evaluable subjects**). [Table 2.](#) and [Figure 1.](#) presents the probability of declaring a dose level safe (unsafe) for a range of true DLT rates for the protocol therapy **based on 6 DLT evaluable subjects (see the triangle symbols)**. For example, the probability of declaring a dose level safe (unsafe) is 89% (11%), 42% (58%), and 11% (89%) if the true DLT rate is 10%, 30%, or 50%, respectively.

**Table 2. Probability of Declaring a Cohort Safe or Unsafe**

True Cohort DLT Probability	Probability Declare Cohort Safe	Probability Declare Cohort Unsafe
10%	89%	11%
20%	66%	34%
30%	42%	58%
40%	23%	77%
50%	11%	89%

Figure 1. Probability of Declaring a Cohort Safe (Unsafe)

**4. Study Endpoints and Covariates**

**4.1 Study Endpoints**

**4.1.1 Primary Endpoints**

- Subject incidence of DLTs

[figure not shown]
**4.1.2 Secondary Endpoints**

- ORR, DOR, TTR, TTP, and PFS using modified irRC-RECIST
- OS

**4.1.3 Safety Endpoints**

- Subject incidence of adverse events and clinical significant laboratory abnormalities

**4.1.4 Exploratory Endpoints**

## 4.2 Planned Covariates

The following covariates may be used to examine clinical activity in subgroups or in multivariate analysis.

- Age at baseline: (2 to < 12 years, 12 to  $\leq$  21 years)
- Sex (female versus male)
- HSV-1 baseline serostatus (positive versus negative)
- Baseline sum of largest diameter of target lesions
- Extent of disease (localised versus metastatic)
- Performance status (Karnofsky/Lansky play scale (70% versus > 70%))
- Prior lines of therapy in the recurrent/metastatic setting (0, 1, 2, > 2)
- Prior surgery for current malignancy (yes versus no)
- Prior radiotherapy for current malignancy (yes versus no)
- Complete surgical resection of all gross diseases (yes versus no)
- Other covariates reported in the literature or from other Amgen studies maybe considered in the analysis as appropriate and if feasible at the time of analysis.

## 5. Hypotheses and/or Estimations

Talimogene laherparepvec injected in pediatric subjects with advanced non-CNS tumors that are amenable to direct injection will be safe as assessed by subject incidence of DLTs and the safety profile.

## 6. Definitions

### 1-year, 2-year survival

The Kaplan-Meier (K-M) estimate of the proportion of subjects alive at 1 year and 2 years, respectively.

### Actual Follow-up Time

Actual follow-up time for a subject is calculated from the first dose to the last on-study date (ie, death date, or date last known to be alive for patients still alive).

### Baseline

Baseline in general refers to study day 1. The baseline value of a parameter (eg., vital signs, laboratory tests, and tumor measurement) is considered to be the latest value prior to receiving any study drug. If a subject did not receive study drug, then the latest value on or prior to the enrollment date is to be used.

### Best overall response (BOR) per Modified irRC-RECIST

Best overall response (BOR) of complete response (CR), partial response (PR), stable disease (SD), progressive disease (PD) or un-evaluable (UE) will be derived based on

investigator assessment using modified irRC-RECIST as defined in protocol Appendix D. Any baseline tumor markers above the ULN must normalize for an overall visit response of CR.

Overall visit response assessments occurring after the start of the first subsequent anticancer therapy, including complete or partial removal/reduction of any target lesion, will not be included. Consecutive confirmation of CR, PR, and PD is required where the second overall response must be at least 28 days from the first, the only exception being when the investigator reports that an initial PD cannot be confirmed due to rapid clinical deterioration. The following will be considered a confirmed PR: CR followed by PR or PR followed by CR.

BOR is defined as the best visit response in the following order: CR, PR, SD, PD, or UE (see [Table 3](#)). BOR is defined as SD if the best overall visit response is an unconfirmed CR or PR, and UE if it is either SD earlier than 49 days after the date of first dosing or an unconfirmed PD when confirmation of PD is required (ie, initial PD without rapid clinical deterioration).

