- The subject, for any reason, requires treatment with another anticancer therapeutic agent for the study disease (other than the exceptions noted in [Section 6.4](#)). In this case, discontinuation from the study treatment occurs immediately upon introduction of the new agent.
- Confirmed PD occurs as defined per modified irRC-RECIST or clinical progression per the investigator.
- A grade 2 or greater immune-mediated adverse event (with the exception of vitiligo) or allergic reactions attributed to talimogene laherparepvec that would require a dose delay of greater than 6 weeks from the date of the planned dose.
 - NOTE: immune-mediated glomerulonephritis, vasculitis, and pneumonitis and exacerbation of psoriasis have been observed in subjects receiving talimogene laherparepvec in clinical trials. Most of these subjects had a history of other autoimmune disease and/or prior treatment with agents that offered plausible alternative etiologies; however, immune-mediated adverse events can potentially involve any organ system.
- Any other talimogene laherparepvec-related non-hematologic or hematologic toxicities grade 3 or greater that, in the opinion of the investigator, would require a dose delay of greater than 6 weeks from the date of the planned dose.
- The subject develops clinical evidence of any systemic herpetic infection (such as encephalitis or disseminated infection).

Approved

- An FCBP subject becomes pregnant or fails to use acceptable method(s) of effective contraception.
- A female subject breastfeeds while on study treatment.
- Concurrent medical illness that, in the judgment of the investigator, would make continued treatment with talimogene laherparepvec dangerous for the subject.
- Subject or legally acceptable representative withdraws consent/assent or wishes to stop the study treatment.

For additional information related to special warnings and precautions for the use of talimogene laherparepvec please refer to the latest version of the [talimogene laherparepvec Investigator's Brochure](#).

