6.9 Excluded Treatments, Medical Devices, and/or Procedures During Study Period

Subjects must not use any of the following therapies during screening or treatment period, unless indicated otherwise:

- other investigational agents or procedures
- concurrent experimental or approved anticancer therapies other than study drug and radiation therapy required for palliation.

In addition, the following are not permitted during the treatment period:

- Immunosuppressive agents with the exception of treatment for adverse events
- If the subject requires corticosteroid dosing for related toxicities, talimogene laherparepvec treatment must be withheld until the corticosteroid dose has decreased to doses acceptable for maintenance physiologic replacement
- Subjects who are receiving talimogene laherparepvec may not receive systemic antiherpetic drugs (eg, acyclovir, valacyclovir, famciclovir), but may receive a topically administered antiherpetic drug more than 20 cm from a talimogene laherparepvec injection site with the exception of treatment for adverse events.
- Childhood vaccinations that contain live attenuated virus

If a subject undergoes any unexpected surgery during the course of the study, all study treatments must be withheld and the investigator or designee should notify the sponsor's medical monitor as soon as possible. Re-exposure to talimogene laherparepvec may occur only if the investigator and sponsor agree that the subject safety will not be compromised.

Subjects in the safety follow-up period who have not demonstrated confirmed disease progression, rapid clinical deterioration, **clinical progression**, or intolerance to talimogene laherparepvec may not receive any experimental or approved antitumor therapies unless the sponsor's medical monitor is consulted and approved.

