If a subject is classified as having PD at a post baseline tumor assessment, then confirmation of PD by a second assessment ≥ 4 weeks (28 days) later in the absence of rapid clinical deterioration (ie, rapid decline in performance status) or symptomatic disease requiring rapid initiation of alternative systemic anti-cancer therapy is required. The definition of confirmation of progression represents a $\geq 20\%$ and at least 5 mm absolute increase in the total tumor burden (ie, the sum of diameters of target lesions plus new measurable lesions) compared to the nadir at 2 consecutive time-points at least 4 weeks (28 days) apart (with the date of progression considered to be the time of the initial evaluation showing PD).

Subjects with a global deterioration of health status requiring discontinuation of treatment without objective evidence of PD at the time should have the reason for treatment discontinuation specified. Every effort should be made to document the objective progression even after discontinuation of treatment.

Subjects who have had a procedure to completely/partially resect a lesion will be evaluated as follows:

The procedure itself and all post-procedure lesion assessments should always be recorded in the case report form (CRF). A completely resected lesion should be assigned a default code of 0 mm (for target lesions) or "absent" (for non-target lesions), except as described below for lymph nodes. A partially resected lesion should be assigned its measurement post-procedure (for target lesions) or "present" (for non-target lesions). If the resected lesion contained no cancer under pathology evaluation, subsequent tumor assessments post-procedure may be used for tumor burden calculations and/or determination of response. If the resected lesion contained cancer or pathology results were unknown, the recorded tumor assessments post-procedure may be used for tumor burden calculations, but determination of response will be considered unevaluable (UE) for response except in the case of PD.

Approved

If the new tumor burden post-procedure is lower than the nadir before the procedure, then the new nadir will be set to the post-procedure tumor burden. Otherwise, the previous pre-procedure nadir will be retained as the nadir. Subsequent assessments for PD will be determined from the nadir.

Target lymph node previously present

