**Table 3. Matrix of Determining BOR per Modified irRC-RECIST**

Visit Overall Response Sequence	Examples		Best Overall Response	Confirmation specifications
* , PD, PD, *  * , PDr, *  PDr = PD with concurrent or subsequent rapid clinical deterioration as the reason for ending radiographic follow-up.	PD, PD PD, SD, PD, PD PDr		PD	Criteria for BOR= CR, PR, or SD not met. The confirmatory PD must be no less than 4 weeks (28 days) later unless there is rapid clinical deterioration; PDr does not require confirmation; a subsequent PD within 28 days will not be valid for confirmation and will be ignored.
* , SD, *  PD	SD UE, SD PD UE, PD		UE	Criteria for BOR=CR, PR, SD, or PD not met. SD must be < 49 days from first dose (or randomization if not treated).

Page 2 of 2

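### The SAP keeps one of Appendix D's two exemptions from confirming PD, does not declare the change, and leaves the PFS and TTP rules open; the protocol's own confirmation rules also conflict

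*SAP*

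**What the plan says.** **Protocol.** Under Confirmation of Disease Progression, Appendix D asks for a second assessment at least 28 days after an initial PD, in the absence of rapid clinical deterioration (explained there as a rapid fall in performance status) "or symptomatic disease requiring rapid initiation of alternative systemic anti-cancer therapy is required". These are two separate waivers. Three other places require confirmation of PD with no waiver: section 7.3.13, the PD row of Table 6, and footnote d of Table 7, both tables being in Appendix D.

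**SAP.** The definition of best overall response (BOR) in Section 6 cites Appendix D as its source. It then requires confirmation, "the only exception being when the investigator reports that an initial PD cannot be confirmed due to rapid clinical deterioration". The same paragraphs make BOR UE for "an unconfirmed PD when confirmation of PD is required (ie, initial PD without rapid clinical deterioration". Table 3 repeats the limit: "PDr = PD with concurrent or subsequent rapid clinical deterioration as the reason for ending radiographic follow-up", and "PDr does not require confirmation; a subsequent PD within 28 days will not be valid for confirmation and will be ignored".

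The DOR definition takes PD from the BOR definition. The PFS definition refers to PD per modified irRC-RECIST and then dates the event at the initial PD when that PD is consecutively confirmed. The TTP definition refers to the first PD per modified irRC-RECIST and has no confirmation wording. Section 11, which lists departures from the protocol, mentions only the DLT analysis set.

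**The concern.** The affected subject has an initial PD and symptoms that call for prompt systemic therapy, but no reported rapid deterioration, and starts that therapy before a confirming scan. The protocol allows for such switches. When another anticancer agent is needed, section 6.2.1.3 says "In this case, discontinuation from the study treatment occurs immediately upon introduction of the new agent". Section 6.9 starts its list with "Subjects in the safety follow-up period who have not demonstrated confirmed disease progression, rapid clinical deterioration" and then names clinical progression as a separate item.

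Once the new therapy starts, a confirming scan is unlikely to exist or to count. Section 7.2.3.2 ends imaging follow-up at new therapy, and the SAP leaves out of BOR "Overall visit response assessments occurring after the start of the first subsequent anticancer therapy".

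Under the Appendix D text this subject has progressed on the date of the first PD scan. Under the SAP the PD may not count. At stake are the BOR categories and, depending on the reading, DOR, PFS and TTP. Two programmers could also derive different PFS from the same definition.

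**Working it through.** The plan gives no figure for this point, so there is none to reproduce. The check has two parts.

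**1. One affected subject, rule by rule**

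| Endpoint | Appendix D text (both waivers) | SAP |
|---|---|---|
| BOR, no qualifying SD or better | PD | UE (explicit) |
| BOR, earlier qualifying SD or response | SD, PR or CR | the same |
| DOR (responders only) | ends at initial PD | censored, or ends at death (by cross-reference to BOR) |
| PFS | event at initial PD | three readings, below |
| TTP | event at initial PD | unchanged, or censored if the BOR rule is carried over |
| ORR | non-responder or responder as before | the same |

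The PFS definition can be read in three ways:
- If PD per modified irRC-RECIST brings in both waivers, nothing changes.
- If the BOR rule is applied, the subject is censored at the PD scan or becomes an event at a later death.
- If consecutive confirmation is taken literally, even the waiver that the SAP keeps is lost.

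**2. Size if the BOR rule is applied to PFS and TTP**

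All inputs are assumptions:
- exponential progression, median 2.5 or 4 months;
- exponential death after progression, median 4 or 8 months;
- share f of detected PDs affected, 5% or 10%;
- median survival m of affected subjects after the PD scan, 1, 2, 4 or 8 months.

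Scans are at Day 50, Day 106, Day 190 and then every 12 weeks. The first two fall at t1 = 49/30.44 = 1.61 and t2 = 105/30.44 = 3.45 months after the first dose.

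*6-month PFS.* An affected subject adds to the curve at month 6 if still alive then:

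shift ≈ f × [D1 × 2^(−(6 − t1)/m) + D2 × 2^(−(6 − t2)/m)],

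where D1 and D2 are the proportions with PD detected at scans 1 and 2. Take medians 4 and 4, so λ = ln 2/4 = 0.1733:
- D1 = 0.1733 × 1.61 × e^(−0.279) = 0.211
- D2 = e^(−0.279) × 0.1733 × 1.84 × e^(−0.319) = 0.175
- With m = 4 and f = 10%: 0.10 × [0.211 × 0.467 + 0.175 × 0.643] = 2.1 points

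Simulation with 400,000 subjects per scenario gives 51.0% to 53.1%, the same shift. Simulated shifts over all scenarios, in points:

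| f | m = 1 | m = 2 | m = 4 | m = 8 |
|---|---|---|---|---|
| 5% | 0.2–0.3 | 0.6–0.9 | 1.0–1.5 | 1.4–2.0 |
| 10% | 0.4–0.6 | 1.2–1.7 | 2.1–3.1 | 2.7–4.0 |

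*6-month TTP, if censored at the PD scan.* Let h1 and h2 be the proportions of those at risk with PD at each scan. Kaplan-Meier gives (1 − h1)(1 − h2) with both waivers and (1 − (1 − f)h1)(1 − (1 − f)h2) without the second. For medians 2.5 and 8, h1 = 0.343 and h2 = 0.379. With f = 10%:
- both waivers: 0.657 × 0.621 = 40.8%
- second waiver dropped: 0.691 × 0.659 = 45.5%

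That is 4.7 points. Over the scenarios the shift is 1.8 to 2.4 points at 5% and 3.6 to 4.8 at 10%.

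*One affected subject.* The step is 1/18 = 5.6 points or 1/24 = 4.2 points. For example, with 6 PDs at the first scan among 18 subjects, PFS after that scan is 12/18 = 66.7% with both waivers and 13/18 = 72.2% if one of them is censored. If that subject dies before month 6, the 6-month difference can vanish. A single trial can therefore move by 0 to 5.6 points (18 subjects) or 0 to 4.2 (24). Scenario averages are 0.5 to 3.9 and 0.4 to 2.9.

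*BOR.* Under these assumptions PD is found at the first scan in 21% to 34% of subjects. UE then replaces PD in 0.05 × 21% = 1.1% to 0.10 × 34% = 3.4% of subjects, or about 0.2 of 18 to 0.8 of 24.

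**The case against.** **The protocol has no single rule for the SAP to depart from.** Section 7.3.13 and Tables 6 and 7 allow no waiver, and Appendix D derives overall response from those tables. This stands, and the protocol conflict is part of the point. It does not clear the SAP, which follows neither the strict text nor the text with two waivers and declares no choice.

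**PFS and TTP may not change at all.** A reader might infer that both are certainly inflated. The documents do not support that: both definitions refer to PD per modified irRC-RECIST, and TTP says nothing about confirmation. Only the BOR effect is explicit, and the DOR effect follows by cross-reference. Zero therefore belongs in both ranges.

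**The safety follow-up scan may confirm the PD.** A reader might infer a fixed interval that is always too short, or always long enough. Neither follows. The interval depends on the date of the last dose, the +7-day visit window and the ±7-day scan window in protocol Table 3. A PD confirmed at least 28 days later and before new therapy is not affected.

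**Investigators may report these cases as rapid deterioration.** Some may, and that would reduce the effect. The result would then depend on how each site words the reason.

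**The size rests on assumed inputs.** It does, and the figures show scale only. For comparison, the exact 95% confidence interval for 7 of 18 is 17% to 64%.

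**Conclusion.** The mismatch is certain from the text: two waivers in the Appendix D paragraph, none in three other protocol places, one in the SAP, and no declaration in Section 11. The explicit consequence is UE in place of PD for an affected subject with no qualifying SD or better. On average that is fewer than one of 18 to 24 subjects under the assumptions above.

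With 5% to 10% of detected PDs affected, 6-month PFS rises by 0 to about 4 points and 6-month TTP by 0 to about 5, with zero where the definition is read to carry both waivers. If PFS is read literally, the same scale applies to the combined share of both exempt groups. Any effect lengthens PFS, TTP or DOR. DOR is not quantified because it needs responders.

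The point is minor. These are descriptive secondary endpoints, and neither ORR nor the primary DLT endpoint is touched. It would be wrong to infer that the efficacy conclusions are unsound.

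**What to change.** Preferred change:
- Add the second Appendix D waiver to the SAP BOR text, the UE rule and the PDr row of Table 3. Identify it by an investigator-reported reason, as PDr already is, and not from subsequent-therapy records alone.
- State in the PFS, TTP and DOR definitions that a PD exempt from confirmation is an event at the initial PD date.
- Reconcile protocol 7.3.13, Table 6 and Table 7 footnote d with the Confirmation of Disease Progression text. Confirmed PD also bears on stopping treatment, so that reconciliation is for the clinical team; this point concerns endpoint derivation only.

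Alternative: declare the narrower rule in SAP Section 11 and add a sensitivity analysis that counts these PDs as events at the initial PD date.

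Cost: SAP wording and one programming condition. The therapy fields in protocol 7.3.11 do not show that symptoms required rapid treatment, so a few site queries may be needed; 11 subjects were enrolled at Amendment 3. Such queries are retrospective and partly subjective in an open-label trial. The CRF is not among the documents, so whether it needs a new reason category is unknown. PFS, TTP and DOR may look slightly less favourable.
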